7.2 Primary Analysis of the Primary Outcome

The primary outcome is patient clinical status 14 days after randomization (on Study Day 15) as assessed with a seven-category ordinal scale (the COVID Ordinal Outcome Scale). The scale consists of the following categories: 1, death; 2, hospitalized, receiving ECMO, invasive mechanical ventilation, or both; 3, hospitalized, receiving noninvasive mechanical ventilation, nasal high-flow oxygen therapy, or both; 4, hospitalized, receiving supplemental oxygen; 5, hospitalized, not receiving supplemental oxygen; 6, not hospitalized, but unable to perform normal activities; 7, not hospitalized, able to perform normal activities.

The primary analysis will be a comparison of the primary outcome between patients randomized to the hydroxychloroquine group versus the placebo group. The comparison will be made using proportional odds regression. The dependent variable will be the primary outcome. Independent variables will include treatment group assignment and the following pre-specified 5 covariates:

- Age at randomization
- Sex
- Clinical status as assessed by the COVID Ordinal Outcome Scale at randomization
- Sequential Organ Failure Assessment (SOFA) score at randomization
- Duration of acute respiratory infection symptoms prior to randomization

The placebo group serves as the referent group for analyses. Because the primary outcome ranges from “death” as the lowest value of 1 to “not hospitalized and without limitations in activities” as the highest value of 7, an odds ratio >1.0 indicates more favorable outcomes with hydroxychloroquine while an odds ratio <1.0 indicates more favorable outcomes with placebo. Results of the primary analysis of the primary outcome will be presented as an adjusted common odds ratio and associated 95% confidence intervals.

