7.4 Effect Modification Analyses of the Primary Outcome

We will examine whether pre-specified baseline variables modified the effect of treatment group on the primary outcome using tests of statistical interaction in a proportional odds regression model. Independent variables will include study group assignment, the potential effect modifier of interest, the interaction between the two, and the same pre-specified covariates used in the primary model. Presence of effect modification will be assessed by reference to the P value for the interaction term, with values less than 0.10 considered to suggest a potential interaction and values less than 0.05 considered to confirm an interaction.

We will examine whether the following pre-specified baseline variables modify the effect of study group on the primary outcome:

1. Clinical status at randomization as assessed by the four categories of the seven-category ordinal outcome scale for which patients could qualify at randomization:
 - a. Receiving ECMO, invasive mechanical ventilation, or both
 - b. Receiving noninvasive mechanical ventilation, nasal high-flow oxygen therapy, or both

- c. Receiving supplemental oxygen
- d. Not receiving supplemental oxygen
2. Located in an intensive care unit at randomization (Yes, No)
3. Sequential Organ Failure Assessment (SOFA) score at randomization
4. Duration of symptoms of acute respiratory infection prior to randomization
5. Age
6. Sex
7. Race and ethnicity

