7.7 Analysis of On-study Variables

Variables that are measured systematically at intermittent time points during the study will be presented at each time they are measured, stratified by randomized group. These analyses will include:

- QTc measurement on Study Day 2 (24-48-hour time window)
- COVID Ordinal Outcomes Scale on Study Days 2, 3, 4, and 5
- SOFA score on Day 3
- S/F ratio / Respiratory SOFA score on Day 3

7.8 Handling of Missing Data.

Primary Outcome. Primary outcome data will be complete for all patients hospitalized through Day 15 because all data needed to classify the primary outcome are available in the medical record. For patients discharge prior to Day 15, data for the primary outcome are collected via a telephone follow-up call. If primary outcome data are missing for patients who left the acute care PETAL hospital prior to Day 15, the following procedures will be used:

- Patients who left the hospital prior to Day 15 and did not have a COVID Ordinal Outcomes Scale collected via phone follow-up at Day 8 (either because they remained in the hospital from the index hospitalization on Day 8 or, if discharge prior to Day 8, were not reached by phone on Day 8), the primary outcome will be coded as a level 6 (not hospitalized with limitation in activity) on COVID Ordinal Outcomes Scale.
- Patients who completed a COVID Ordinal Outcomes Scale by phone follow-up on Day 8 will have the level from the Day 8 assessment carried forward to the Day 15 primary outcome assessment.

Covariates. We expect missing data for the pre-specified covariates in the proportional odds and logistic regression models to be rare. If missing data do exist for these covariates, values will be imputed using simple imputation of the median value from the trial population with non-missing data.

Secondary Outcomes. Data will not be imputed for secondary outcomes. The frequency of missing data will be reported.

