If patients remained in the hospital, outcome assessment was performed by review of the electronic health records. For patients who were discharged prior to 14 days after randomization, study staff called patients or their surrogates to obtain patients’ clinical status (“all-location outcome”). To distinguish between category 6 (not hospitalized, but unable to perform normal activities) and category 7 (not hospitalized, able to perform normal activities), study personnel assessed the patient’s performance of “usual activities” with questions consistent with validated health status measures. An answer of “no problems doing my usual activities” resulted in assignment to category 7.

SOFA Score Calculation

The SOFA score at baseline (pre-randomization) was used as a co-variable in the regression models for the primary and secondary outcomes. The SOFA score was calculated using the definitions based on the Third International Consensus Definitions for Sepsis and Septic Shock (Sepsis-3).⁷ The SOFA score was calculated using data available in the 24 hours prior to randomization. We recorded the following data for SOFA score calculation: lowest PaO₂ and FIO₂ at the time of the lowest PaO₂ measurement; lowest SpO₂ and FIO₂ at the time of the lowest SpO₂ measurement; lowest platelet count; highest total bilirubin concentration; lowest Glasgow Coma Score; lowest mean arterial pressure; receipt and dose of inotropes/vasopressors, including dobutamine, dopamine, epinephrine, norepinephrine, phenylephrine, and vasopressin; highest creatinine; urine output; highest INR.

For calculation of the respiratory component of the SOFA score, if recorded, FiO₂ was used in the calculation of P:F or S:F ratio. If no FIO₂ was recorded, FiO₂ was estimated with the following equation: $0.21 + (\text{supplemental oxygen flow rate in liters/minute}) * 0.03$. If PaO₂ was recorded, the recorded PaO₂ value was used in the calculation of P:F ratio and respiratory SOFA score. If no PaO₂ value was recorded, respiratory SOFA score was classified by SpO₂ and SpO₂:FiO₂ ratio according to the table below based on the validated technique described by Pandharipande⁸:

Respiratory SOFA Score assignment based on SpO₂ and FIO₂ values when no PaO₂ is recorded	
Values	Respiratory SOFA Score Assignment
SpO ₂ ≥95% and FiO ₂ =0.21 (room air)	0
If SpO ₂ <95% or FiO ₂ >0.21, calculate the SpO ₂ :FiO ₂ ratio and assign respiratory SOFA score based on the thresholds below:	
SpO ₂ : FiO ₂ ≥357	1

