For calculation of oxygen-free days, supplemental oxygen was defined as oxygen administered by nasal cannula, face mask, high-flow nasal cannula, non-invasive ventilation, or invasive ventilation. Positive airway pressure (CPAP, BiPAP) provided solely at night as treatment for sleep-disordered breathing (e.g. obstructive sleep apnea) was not considered supplemental oxygen. Oxygen-free days were calculated as the number of whole calendar days alive and not receiving supplemental oxygen between randomization and study day 29. Patients who died before Day 29 received a value of 0. If a patient survived through study day 29 and never received supplemental oxygen, the number of oxygen-free days was 28. If a patient received supplemental oxygen and survived through study day 28, the number of oxygen free-days was calculated as 28 minus the number of calendar days from the first day on which the patient received supplemental oxygen until the last day on which the patient received supplemental oxygen. Days on which the patient did not receive supplemental oxygen that occurred between days on which the patient received supplemental oxygen did not count towards the number of oxygen free days. Data on oxygen use were censored at hospital discharge and the last observed status was carried forward (“in-hospital outcome”). That is, if the patient was receiving supplement oxygen at hospital discharge, the analysis assumed they continued to receive supplemental oxygen through Study Day 29. If the patient was not receiving supplemental oxygen at hospital discharge, the analysis assumed the patient continued not to receive supplemental oxygen through Study Day 29.

Ventilator-free days to Day 28

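### The SAP's fallback estimate of FiO2 has no ceiling and no stated device or flow range, so at flows above 26.3 L/min it gives impossible values and can overstate the respiratory SOFA score

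*SAP*

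**What the plan says.** The rule is in SAP Appendix B, under SOFA Score Calculation. A recorded FiO2 takes precedence and "was used in the calculation of P:F or S:F ratio". Where none was recorded, FiO2 "was estimated with the following equation": 0.21 + 0.03 × "supplemental oxygen flow rate in liters/minute". Neither the SAP nor the protocol attaches a maximum, a flow range or a list of devices to this equation.

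If a PaO2 exists, the respiratory score comes from the P:F ratio. If not, it comes from a printed S:F table: 357 or more scores 1, 214 to below 357 scores 2, 89 to below 214 scores 3, and below 89 scores 4. Room air with SpO2 of at least 95% scores 0. If neither ratio is available, the trial median respiratory score is imputed.

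The score is used in these places:
- SAP 7.2 lists "Sequential Organ Failure Assessment (SOFA) score at randomization" among the five covariates of the primary model. SAP 7.5 carries the same covariates into the adjusted secondary models.
- SAP 7.4 lists baseline SOFA among seven effect modifiers.
- SAP 7.7 presents "S/F ratio / Respiratory SOFA score on Day 3" by randomized group, together with the Day 3 SOFA score.

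High-flow patients are in scope: one of the four baseline categories in SAP 7.4 is "Receiving noninvasive mechanical ventilation, nasal high-flow oxygen therapy, or both".

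**The concern.** FiO2 is a fraction and cannot exceed 1.0, but the equation is linear in flow and unbounded. It behaves sensibly at conventional flows and fails at the flows one would expect on a high-flow device. The documents do not describe how such devices work. If, as I assume, inspired fraction and flow are set separately, the equation does not describe them at any flow.

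The existing safeguard does not catch the failure. Median imputation applies only when no ratio is available, and an impossible FiO2 still yields a ratio. The affected record therefore passes through with a low S:F and a high respiratory score, and once the flow is high enough that score no longer depends on the patient's saturation.

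At stake is the accuracy of baseline SOFA as a covariate and as a candidate effect modifier. The Day 3 SOFA and S/F summaries are also at stake if they are derived in the same way.

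**Working it through.** The plan states no sample size, power or error figure that depends on this rule, so there is nothing of its own to reproduce. The check evaluates the rule directly.

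**Inputs.** The equation and the cut-offs 357, 214 and 89 are from SAP Appendix B. High-flow rates of 30 to 60 L/min are my assumption. True FiO2 values of 0.3 to 1.0 are also assumed, to show the range.

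**Flow at which the estimate becomes impossible.** 0.21 + 0.03 × L > 1.0 gives L > (1 − 0.21)/0.03 = 26.3 L/min.

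**Flow at which score 4 is returned.** S:F < 89 requires L > (SpO2/89 − 0.21)/0.03:
- SpO2 90%: 26.7 L/min
- SpO2 92%: 27.5 L/min
- SpO2 96%: 29.0 L/min
- SpO2 100%: 30.45 L/min

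Above about 30.5 L/min every saturation scores 4. Between 26.3 and 30.5 L/min the FiO2 is already impossible, but score 3 can still occur at higher saturations.

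**Values by flow.**

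| Flow (L/min) | Estimated FiO2 | S:F (score) at SpO2 92% | S:F (score) at SpO2 100% |
|---|---|---|---|
| 15 | 0.66 | 139.4 (3) | 151.5 (3) |
| 30 | 1.11 | 82.9 (4) | 90.1 (3) |
| 40 | 1.41 | 65.2 (4) | 70.9 (4) |
| 50 | 1.71 | 53.8 (4) | 58.5 (4) |
| 60 | 2.01 | 45.8 (4) | 49.8 (4) |

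With SpO2 100% the lowest S:F that can exist is 100/1.0 = 100, so every S:F in the last column from 30 L/min up is unattainable.

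**Size of the error, SpO2 92% at 40 L/min.**
- As written: 92/1.41 = 65.2, score 4.
- Capped at 1.0: 92/1.0 = 92, score 3.
- True FiO2 0.5 (assumed): 92/0.5 = 184, score 3.
- True FiO2 0.4 (assumed): 92/0.4 = 230, score 2.

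**Cases with no error.**
- SpO2 85% with true FiO2 1.0: S:F is 85, score 4 either way.
- SpO2 99% at 30 L/min: 99/1.11 = 89.2, score 3. With true FiO2 0.5, 99/0.5 = 198, also score 3.

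Over true FiO2 of 0.3 to 1.0, the overstatement is therefore 0 to 2 points. At FiO2 0.3 even SpO2 100% gives 100/0.3 = 333, still score 2.

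**Effect of a cap alone.** At 30 to 60 L/min, any SpO2 of 89% or more would score 3. That removes the impossible values but remains 1 point too high when the true FiO2 was 0.4.

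Where a PaO2 was recorded without an FiO2, the same estimate enters the P:F ratio. The documents print no P:F cut-offs, so I have not sized that case.

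**The case against.** The strongest reply is that the failing case may be empty. The equation is only a fallback, and FiO2 at the lowest PaO2 and at the lowest SpO2 is a listed data item. On a device where FiO2 is set, there should be a value to chart. This stands as a limit on scope: nothing in the documents shows how many high-flow patients, if any, lack a recorded FiO2.

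The second reply is that supplemental oxygen here means conventional oxygen, because the ordinal scale puts high flow in a separate category. That reading is possible, but Appendix B does not state it and elsewhere uses the term more broadly. For oxygen-free days it covers "oxygen administered by nasal cannula, face mask, high-flow nasal cannula, non-invasive ventilation, or invasive ventilation". That definition is scoped to one outcome, but the time-to-recovery rule points the same way. It gives 0.0 days to a patient who never received supplemental oxygen, so on the narrow reading someone treated only with high flow would count as recovered at randomization. A programmer could reasonably enter high-flow rates.

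The third reply is that the consequence is small. That also stands. Baseline SOFA is measured before randomization, and the primary model also adjusts for the baseline ordinal category, which separates the non-invasive and high-flow group from the others.

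A reader might infer that every high-flow patient is forced to the worst respiratory score, or that each is wrong by a fixed 1 to 2 points. The documents support neither. The rule needs an unrecorded FiO2, the S:F table also needs an absent PaO2, and the error can be zero.

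**Conclusion.** The point holds as a minor defect. The rule as written returns an impossible FiO2 above 26.3 L/min and respiratory SOFA 4 at any SpO2 above about 30.5 L/min, and no safeguard in the SAP stops it. On the assumed 30 to 60 L/min and true FiO2 of 0.3 to 1.0, the respiratory score is overstated by 0 to 2 points in a patient to whom the fallback is applied. The number of such patients is unknown. Flows up to 15 L/min give possible values (0.66 or less).

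The effect is added error in the baseline SOFA covariate and in the SOFA effect-modification analysis. It reaches the Day 3 SOFA and S/F summaries only if the same derivation is used there. Appendix B describes the 24 hours before randomization, and SAP 7.7 gives no Day 3 derivation.

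A reader might go further and infer that the primary treatment comparison is biased. The documents do not support that: the error sits in a pre-randomization covariate and does not depend on assigned group. No sample size or stopping rule is touched.

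**What to change.** In SAP Appendix B:
1. Cap the estimated FiO2 at 1.0.
2. Restrict the equation to conventional low-flow oxygen, or to a stated flow range.
3. For high-flow, non-invasive or invasive support, use the set FiO2 charted at the time of the lowest SpO2 or PaO2. If none exists, treat the ratio as missing under the existing median rule.
4. State whether the Day 3 SOFA and S/F use the same derivation.

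Do not substitute the highest FiO2 collected under Protocol 6.1. It covers the 12 hours before enrollment, while SOFA uses the 24 hours before randomization. Pairing a highest FiO2 with a lowest SpO2 from another time can lower S:F artificially.

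The cost is a few sentences in the SAP, and the cap is one line of derivation code. The device at the time of the lowest SpO2 is not among the SOFA inputs that Appendix B lists. If it cannot be recovered from other fields, a flow range is the simpler restriction. The downside is that a few more respiratory scores may be median-imputed, and for a high-flow patient the trial median may itself be wrong.

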- Safety Outcomes: seizure, atrial or ventricular arrhythmia, cardiomyopathy, cardiac arrest, aspartate aminotransferase or alanine aminotransferase levels that are greater than twice the local upper limit of normal, acute pancreatitis (defined by a clinically obtained lipase level above the local upper limit of normal), stage II or greater acute kidney injury according to KDIGO criteria³⁴, receipt of new renal replacement therapy, symptomatic hypoglycemia, neutropenia, lymphopenia, anemia, thrombocytopenia, or severe dermatologic reaction (e.g., Steven's Johnson Syndrome)
- Patient destination at discharge

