SpO ₂ : FiO ₂ ≥214 and <357	2
SpO ₂ : FiO ₂ ≥89 and <214	3
SpO ₂ : FiO ₂ <89	4

When no P:F or S:F ratio is available, the respiratory SOFA score was imputed as the median observed value in the patients in the trial with non-missing values, consistent with the approach to missingness for other variables.

Definition of Secondary Outcomes

Time to Recovery

Recovery was defined as reaching category 5, 6, or 7 on the seven-category COVID Ordinal Outcome Scale. A patient could reach category 5, 6, or 7 on the seven-category COVID Ordinal Outcome Scale either by (a) being discharged from the hospital or by (b) being liberated from supplemental oxygen for the final time during the index hospitalization. Time to recovery was defined as the time between randomization and the first of either hospital discharge or liberation from supplemental

oxygen for the final time during the index hospitalization. Time to recovery was an “in-hospital outcome” and did not reflect information on receipt of supplemental oxygen, rehospitalization, or death after discharge from the index hospitalization.

For a patient who was not receiving supplemental oxygen at the time of randomization, and never received supplemental oxygen during the index hospitalization, the time to recovery was 0.0 days. For a patient who received supplemental oxygen at any time between randomization and discharge from the index hospitalization, but was not receiving supplemental oxygen at the time of discharge from the index hospitalization, the time to recovery was the time from randomization to the time of final receipt of supplemental oxygen during the index hospitalization. For a patient who was receiving supplemental oxygen at the time of discharge from the index hospitalization, the time to recovery was the time from randomization to the time of discharge from the index hospitalization. Patients who remained hospitalized and receiving supplemental oxygen 28 days after randomization were not considered to have experienced recovery. All patients who died prior to discharge from the index hospitalization were not considered to have experienced recovery. Patients who did not experience recovery were awarded a value for the outcome of time to recovery of 28.0 days.

All-location, all-cause 14-day mortality

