Ventilator-free days to day 28 was defined as the number of whole calendar days alive and breathing without invasive mechanical ventilation from 00:00 on the day of randomization through Study Day 29. Patients who died before Study Day 29 received a value of 0. If a patient survived to the first of discharge or Study Day 29 and never received invasive mechanical ventilation, the number of VFDs was 28. If a patient received invasive mechanical ventilation and survived to the first of hospital discharge or Study Day 28, the number of VFDs was calculated as 28 minus the number of calendar days from the first day on which the patient received invasive mechanical ventilation until the last day on which the patient received invasive mechanical ventilation. Days on which the patient did not receive invasive mechanical ventilation that occurred between days on which the patient received mechanical ventilation did not count towards the number of VFDs. Data on ventilation were censored at hospital discharge and the last observed status was carried forward (“in-hospital outcome”). That is, if the patient was receiving invasive mechanical ventilation at hospital discharge, the analysis assumed they continued to receive invasive mechanical ventilation through Study Day 29. If the patient was not receiving invasive mechanical ventilation at hospital discharge, the analysis assumed the patient continued not to receive invasive mechanical ventilation through Study Day 29.

Vasopressor-free days to Day 28

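### Time to recovery counts any index discharge as recovery, so a patient who leaves on invasive ventilation or ECMO, or is transferred to another hospital on advanced support, is scored as recovered while possibly still at level 2 or 3

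*SAP*

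**What the plan says.** Time to recovery is a secondary outcome in Protocol 5.2 and SAP 6.2. SAP Appendix A assigns it a proportional odds model with the pre-specified covariates.

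SAP Appendix B says recovery means reaching category 5, 6 or 7, and that a patient can get there "by (a) being discharged from the hospital or by (b) being liberated from supplemental oxygen for the final time during the index hospitalization". For those still on oxygen when they leave, the rule begins "For a patient who was receiving supplemental oxygen at the time of discharge from the index hospitalization, the time to recovery was the time"; the interval ends at index discharge. The outcome "did not reflect information on receipt of supplemental oxygen, rehospitalization, or death after discharge from the index hospitalization".

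Two groups are not recovered and receive 28.0 days: "Patients who remained hospitalized and receiving supplemental oxygen 28 days after randomization were not considered to have experienced recovery", and "All patients who died prior to discharge from the index hospitalization were not considered to have experienced recovery". No other exception appears in either document. Protocol 5.2 carries the same earlier-of-two rule.

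Two neighbouring definitions in SAP Appendix B bear on this. For oxygen-free days, "supplemental oxygen was defined as oxygen administered by nasal cannula, face mask, high-flow nasal cannula, non-invasive ventilation, or invasive ventilation". For ventilator-free days, "if the patient was receiving invasive mechanical ventilation at hospital discharge, the analysis assumed they continued to receive invasive mechanical ventilation" through Study Day 29.

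**The concern.** The operational rule and the concept behind it can part company. Levels 2 and 3 of the scale describe a hospitalized patient on invasive ventilation or ECMO, or on non-invasive ventilation or high-flow oxygen. A patient moved to another acute-care hospital on such support is still hospitalized and still at level 2 or 3. If that move counts as index discharge, the rule records recovery at the hour of departure.

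The proportional odds model uses the ordering of the values. A misplaced patient therefore moves from the worst value, 28.0 days, to the day of departure, ahead of anyone weaned from oxygen later. If such departures differed between arms, the estimated effect on this outcome would shift for a reason unrelated to recovery.

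**Working it through.** The plan gives no rate, power or effect size for time to recovery, so there is no stated figure to reproduce. The check applies the scoring rules to example patients and then sizes the effect under stated assumptions.

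**Step 1: score example patients under SAP Appendix B**, assuming that transfer ends the index hospitalization.

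| Patient | Scale level on leaving | Time to recovery | Other outcomes |
|---|---|---|---|
| A: ventilated from Study Day 1, transferred still ventilated to another acute-care hospital at 14 days | 2 | 14.0 | 0 ventilator-free and 0 oxygen-free days if alive to Day 29, because support is carried forward |
| B: transferred on high-flow oxygen at 2 days, on oxygen since Study Day 1 | 3 | 2.0 | 0 oxygen-free days, by the same carry-forward |
| C: on low-flow oxygen in hospital, weaned for good at 20 days | 5 | 20.0 | 28 ventilator-free days if never ventilated |

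A and B rank ahead of C on time to recovery. A has the worst possible ventilator-free-day value and C the best. Had A stayed in the study hospital on the ventilator to 28 days, the score would be 28.0. The 14.0-day difference comes from a change of building.

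**Step 2: how many patients.** The documents do not say. The only related figure is Protocol 7.1, Table 1: 5.8% on invasive ventilation at Day 15, taken from an earlier network trial in a different population.

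- 0.058 × 510 = 29.6 patients.
- If 10% to 20% of them leave still ventilated (assumption): 2.96 to 5.9, so about 3 to 6 patients.

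This is an order of magnitude only. Patients still ventilated in the study hospital on Day 15 who leave later score 14 days or more. Those who leave earlier are not in this base.

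**Step 3: effect on the odds ratio.** Assumed inputs: 255 per arm; under the stricter scoring, 22, 14, 14, 10, 8, 6, 4 and 2% of placebo patients recover at days 0, 3, 6, 9, 12, 16, 20 and 24, and 20% do not recover. Affected patients are moved from 28.0 to about day 12. A large-sample proportional odds model without covariates is then fitted; an odds ratio above 1 means faster recovery with hydroxychloroquine.

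| Share moved, placebo / hydroxychloroquine | Patients of 510 | True 1.0 becomes | True 1.8 becomes |
|---|---|---|---|
| 1% / 1% | 5 | 1.000 | 1.809 |
| 3% / 3% | 15 | 1.000 | 1.827 |
| 5% / 5% | 26 | 1.000 | 1.845 |
| 3% / 1% | 10 | 0.969 | 1.768 |
| 1% / 3% | 10 | 1.032 | 1.868 |
| 5% / 2% | 18 | 0.953 | 1.758 |
| 2% / 5% | 18 | 1.049 | 1.909 |

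Imbalances of 2 to 3 points mean 0.02 × 255 = 5.1 to 0.03 × 255 = 7.7 more patients in one arm than the other. With the smaller counts from Step 2, split 4 placebo to 2 hydroxychloroquine, a true 1.0 becomes 0.988 if affected patients sit at day 12 and 0.971 if they sit at day 3. Split 2 to 1, it becomes 0.994 and 0.985.

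**The case against.** The strongest reply is that this is a declared definition. Protocol and SAP give the same rule, and the SAP says openly that the outcome ignores events after discharge. That stands: there is no conflict between the two documents, and a change touches a protocol secondary outcome. It does not remove the tension inside Appendix B between the stated concept and the rule.

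Second, the transfer case depends on an undefined term. Neither document says whether transfer ends the index hospitalization. Protocol 6.3.1 speaks of discharge from the study hospital, and SAP 7.8 of leaving the acute care network hospital. Both lean towards transfer ending it, but neither settles it. This also stands, and is itself a reason for a clarifying sentence.

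Third, the carry-forward sentence for ventilation may be template wording, since a parallel sentence covers vasopressors at discharge. It shows that the SAP has a rule for such patients, not that many were expected.

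Fourth, other outcomes still register these patients: the all-location ordinal scale at Days 15 and 29, mortality, and the free-day outcomes. That limits the damage to one secondary outcome.

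A reader might also infer more than the documents support:

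- That hospice discharges are misclassified. Levels 6 and 7 require only that the patient is not hospitalized, so a patient discharged to hospice at home is at level 6 until death.
- That every patient sent to a long-term acute care hospital is really at level 2. The documents do not say whether such a patient counts as hospitalized.
- That the sickest patients appear as early recoveries in number. No frequency is given, and the 5.8% figure cannot supply departures before Day 15.
- That the error must oppose the true effect. Direction and size depend on which arm has more such departures.

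**Conclusion.** The point holds in a limited form. Nothing in either document stops a patient who leaves on invasive ventilation or ECMO, or who is transferred to another acute-care hospital on non-invasive ventilation or high-flow oxygen, from being scored as recovered on departure. For an acute-care transfer that contradicts the level 5 to 7 definition, provided the transfer ends the index hospitalization. For any departure on invasive ventilation it also sits badly with the ventilator-free-day rule.

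The likely size is small: a few patients if the assumed 10% to 20% is about right. Equal shares create no false effect under the null. Even the larger assumed imbalances of 2 to 3 points move a true odds ratio of 1.0 only to about 0.95 to 1.05. The primary outcome and stopping rules do not use this definition. It is worth correcting because the misclassification is avoidable and the needed data are largely collected, not because it threatens the trial's main conclusion.

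**What to change.** In SAP Appendix B, with matching wording in Protocol 5.2 and the study summary:

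1. State that transfer to another acute-care hospital does not end the index hospitalization for this outcome.
2. State that discharge while receiving invasive ventilation or ECMO, or acute-care transfer on non-invasive ventilation or high-flow oxygen, is not recovery. Score 28.0 days unless a follow-up call shows level 5 to 7, in which case use that call's study day, converted to days since randomization (study day minus 1) and capped at 28.0. Only the Day 8 and Day 15 calls can then give a value below 28.0.
3. Keep ordinary discharge on low-flow oxygen as recovery, including return to a prior residence or long-term acute care hospital on baseline oxygen.
4. Add a sensitivity analysis that scores hospice discharges and all-location deaths by Day 29 as 28.0 days.
5. Report counts of all these discharges by arm.
6. Leave the time-to-hospital-discharge outcome unchanged; it measures index discharge as such.

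Protocol 6.2 already collects first and final dates of each support and "Patient destination at discharge", and the calls in Protocol 6.3.1 record death and the ordinal scale. The cost is wording, derivation code and a minor clarification of a protocol secondary outcome. There are two limits. Protocol 6.2 lists no destination categories, so check that the field identifies acute-care transfer and hospice. And SAP 7.5 says detailed support data stop at index discharge, so a few patients with unknown later status will score 28.0 days, and call dates will overstate recovery time for others.
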